#### **4.12.3 Biomarkers**

Analyses of biomarkers will be defined in a separate analysis plan.

#### **4.12.4 Genetic Research**

Analyses of genetics will be defined in a separate analysis plan, if deemed necessary.

### **4.13 Determination of Sample Size**

The sample size assumptions outlined below for the primary objective assume that all doses are carried through to the end of the study, although there is the option to stop randomisation to doses following the interim analyses if clinical response criteria are not met, therefore the sample size gives the minimum number of subjects per arm.

The following sample size assumptions have been applied for the primary analysis and the dose response analysis:

#### **4.13.1 Primary Analysis**

The sample size for the primary analysis and hence the overall sample size for the study is based on detecting a 30% difference from placebo in the proportion of subjects in remission (DAS28 score <2.6) at Week 24 of the 52 week double-blind treatment period for each GSK3196165 dose.

Using a Fisher's exact test, a sample size of 35 subjects per arm will provide approximately 90% power to detect a difference of 30% in the proportion of subjects in remission between each GSK3196165 dose (33%) and placebo (3%) at the two-sided  $\alpha=0.05$  level at 24 weeks. The placebo rate of 3% is based on a literature review of current therapies presenting DAS28(CRP) remission results. No adjustments will be made to the sample size to account for the multiple doses in this Phase 2 study.

The least significant difference this sample size will detect is an approximate 17% difference from placebo.

The sample size will not be increased to account for dropouts and all dropouts within the treatment period will be classed as non-remitters for the primary analysis.

#### **4.13.2 Dose Response Analysis**

It is estimated the dose response analysis can be conducted once a minimum of 15 subjects in each of the six treatment groups complete 12 weeks of treatment. Other analyses at earlier time points may also be conducted. The sample size has been estimated using simulation.

The anticipated dose response curve assuming the numbers summarised below, and the precision around it was obtained through 100000 simulations where the following changes from baseline in DAS28(CRP) have been assumed at each dose level, with a between subject standard deviation of 1 (based on Phase 2 data in a DMARD-IR population):

**Table 9 Assumed Change from Baseline in DAS28(CRP) Responses at 12 Weeks**

Treatment	Placebo	22.5 mg	45 mg	90 mg	135 mg	180 mg
DAS28(CRP) change from baseline	-1.0	-1.54	-1.83	-2.1	-2.24	-2.32
N	N=15	N=15	N=15	N=15	N=15	N=15

The assumed change from baseline in DAS28(CRP) of 1.0 points on the placebo arm is based on a review of studies in a DMARD-IR population.

It is expected that the shape of the dose response curve will be sigmoidal and the data for the DAS28(CRP) change from baseline was simulated assuming the following three parameter Emax model:

$$Y = E_0 + E_{\max} * [D_i / \{ ED_{50} + D_i \}]$$

[figure not shown]
Where  $E_0$  is the minimum dose effect,  $E_{\max}$  is the maximum achievable effect above  $E_0$ ,  $ED_{50}$  is the dose at half  $E_{\max}$  and  $D_i$  are the doses = 0, 22.5, 45, 90, 135 and 180 mg.  $Y$  is a measure of DAS28(CRP) change from baseline. In this case the  $E_0$  is the assumed effect with Dose=0 (placebo) which is -1.0 and the  $E_{\max}$  is taken as -1.65, the maximum achievable effect above placebo.

[Figure 1](#) shows the first 100 prediction curves (from 100000 simulations) and the overall median curve with the assumptions outlined above, illustrating the anticipated dose response curve with 15 subjects per arm. The black vertical intervals around each dose represent the change from baseline in DAS28(CRP) that are the 2.5 and 97.5 percentile values from all simulations.

The following table displays the proportion of simulations that are within a precision of 0.45 units in the change from baseline in DAS28(CRP) at each dose, with 15 subjects per arm. For the 135mg dose this is 98.9%.

**Table 10 Proportion of Simulations that are Within a Precision of 0.45 Units in the Change from Baseline in DAS28(CRP) at each Dose**

22.5 mg	45 mg	90 mg	135 mg	180 mg
90.4%	97.9%	98.8%	98.9%	95%

**Figure 1 Plot of the First 100 Prediction Curves with the Overall Median Curve at the Dose Response Analysis**

#### 4.13.3 Sample Size Sensitivity for Primary Analysis

The power of the study will be affected by changes from the assumed remission rate and the table below shows the effect on power under varying remission rates on both MTX and GSK3196165 assuming a fixed sample size of 35 per arm.

**Table 11 Power for Remission at 24 Weeks under Varying Remission Rates on MTX and GSK3196165:**

MTX Remission Rate	GSK3196165 Remission Rate		
	25%	33%	45%
3%	69%	90%	99%
10%	27%	57%	89%
15%	12%	32%	73%

#### 4.13.4 Sample Size Sensitivity for Dose Response Analysis

A key aspect of determining the sample size to assess dose response is the precision around the model estimates of the response (change from baseline on the DAS28(CRP)). The following Table outlines the proportion of simulations that are within a precision of 0.45 units in the change from baseline in DAS28(CRP) at the 22.5 mg and 135 mg dose groups for different estimates of the sample size and different values of the SD estimate, following 10000 simulations.

**Table 12 Proportion of Simulations that are Within a Precision of 0.45 Units in the Change from Baseline in DAS28(CRP) at the 22.5 and 135 mg Dose Groups Following 10000 Simulations**

SD Estimate	N per Treatment group	Proportion	
		22.5 mg	135 mg
0.7	10	98.4%	99.7%
	13	99.8%	99.9%
	15	99.9%	99.9%
1.0	10	61.5%	96.5%
	13	81.8%	98.2%
	15	90.3%	98.9%
1.3	15	52.2%	94.7%
	20	73.4%	97.5%
	25	89.5%	98.4%

Table 10 gives the 2.5 and 97.5 percentiles around the median estimates of response (Change from baseline in DAS28(CRP)) at each dose level assuming 20 subjects per treatment group for differing values of the SD estimates following 10000 simulations.

**Table 13 2.5 and 97.5 Percentiles around the Median Estimates of Response at each Dose Level Following 10000 Simulations**

SD Estimate	Placebo	22.5 mg	45 mg	90 mg	135 mg	180 mg
0.7	-1.33, -0.64	-1.83, -1.33	-2.03, -1.61	-2.27, -1.92	-2.44, -2.03	-2.59, -2.08
1.0	-1.44, -0.49	-1.93, -1.24	-2.11, -1.54	-2.33, -1.85	-2.52, -1.95	-2.69, -1.99
1.3	-1.54, -0.34	-2.02, -1.17	-2.18, -1.47	-2.41, 1.78	-2.60, -1.88	-2.80, -1.93

#### 4.14 Changes in the Conduct of the Study or Planned Analysis

Continuous efficacy results for subjects who rescue to 180 mg dose or exceed the amount of allowed corticosteroid use will be set to missing as opposed to an observed cases analysis.

The exploratory endpoint ‘time to first sustained ( $\geq 24$  continuous weeks) DAS28(CRP) remission’ was modified to the proportion of subjects with sustained DAS28(CRP) remission including the Week 52 visit. Similarly, the definition of ‘Major Clinical Response’ was modified to achieving ACR70 for  $\geq 24$  continuous weeks including the Week 52 visit.

The exploratory endpoint ‘Time to sustained ( $\geq 24$  weeks) discontinuation of all systemic corticosteroids administered for RA’ will not be investigated. Instead a summary of corticosteroid concomitant medications will be converted to prednisone equivalent units, and the change from baseline in average daily prednisone dose will be summarised by visit. The number and percentage of subjects with  $\geq 25\%$  decrease from baseline to  $\leq 7.5$  mg/day will be summarised at Weeks 12, 24, 36, 48 and 52.

## 6 Appendix

### 6.1 Appendix A: Opportunistic Infections: MedDRA Preferred Terms

Opportunistic Infections: MedDRA Preferred Terms	
AIDS retinopathy	Herpes pharyngitis
Acid fast bacilli infection	Herpes sepsis
Acinetobacter bacteraemia	Herpes simplex
Acinetobacter infection	Herpes simplex cervicitis
Acquired immunodeficiency syndrome	Herpes simplex hepatitis
Actinomycosis	Herpes simplex meningoencephalitis
Actinomycotic abdominal infection	Herpes simplex otitis externa
Actinomycotic pulmonary infection	Herpes simplex test positive
Acute HIV infection	Herpes simplex virus conjunctivitis neonatal
Acute hepatitis B	Herpes simplex visceral
Acute hepatitis C	Herpes virus infection
Adrenal gland tuberculosis	Herpes zoster
Arthritis fungal	Herpes zoster cutaneous disseminated
Arthritis salmonella	Herpes zoster disseminated
Aspergilloma	Herpes zoster infection neurological
Aspergillosis oral	Herpes zoster meningitis
Aspergillus infection	Herpes zoster meningoencephalitis
Asymptomatic HIV infection	Herpes zoster meningomyelitis
Asymptomatic viral hepatitis	Herpes zoster necrotising retinopathy
Atypical mycobacterial infection	Herpes zoster oticus
Atypical mycobacterial lower respiratory tract infection	Herpes zoster pharyngitis
Atypical mycobacterial lymphadenitis	Histoplasmosis
Atypical mycobacterial pneumonia	Histoplasmosis cutaneous
Atypical mycobacterium pericarditis	Histoplasmosis disseminated
Bacterial parotitis	Human T-cell lymphocytic virus type II infection
BK virus infection	Human T-cell lymphotropic virus infection
Biliary tract infection cryptosporidial	Human T-cell lymphotropic virus type I infection
Biliary tract infection fungal	Human polyomavirus infection
Blastomycosis	Immune reconstitution inflammatory syndrome associated tuberculosis
Bone tuberculosis	Intestinal tuberculosis
Brachyspira infection	JC virus granule cell neuronopathy
Brain empyema	JC virus infection

Opportunistic Infections: MedDRA Preferred Terms	
Bronchitis fungal	Joint tuberculosis
Bronchopulmonary aspergillosis	Kaposi's sarcoma
Bronchopulmonary aspergillosis allergic	Kaposi's sarcoma AIDS related
Brucella sepsis	Kaposi's varicelliform eruption
Brucellosis	Leptotrichia infection
Candida endophthalmitis	Listeria encephalitis
Candida infection	Listeria sepsis
Candida osteomyelitis	Listeriosis
Candida pneumonia	Lower respiratory tract herpes infection
Candida retinitis	Lower respiratory tract infection fungal
Candida sepsis	Lymph node tuberculosis
Cerebral aspergillosis	Lymphadenitis fungal
Cerebral fungal infection	Lymphoma AIDS related
Cerebral toxoplasmosis	Male genital tract tuberculosis
Choroid tubercles	Meningitis aspergillus
Chronic hepatitis	Meningitis candida
Chronic hepatitis C	Meningitis coccidioides
Coccidioides encephalitis	Meningitis cryptococcal
Coccidioidomycosis	Meningitis fungal
Colitis herpes	Meningitis herpes
Congenital HIV infection	Meningitis histoplasma
Congenital cytomegalovirus infection	Meningitis listeria
Congenital hepatitis B infection	Meningitis salmonella
Congenital herpes simplex infection	Meningitis toxoplasmal
Congenital toxoplasmosis	Meningitis tuberculous
Congenital tuberculosis	Meningoencephalitis herpes simplex neonatal
Congenital varicella infection	Meningoencephalitis herpetic
Conjunctivitis tuberculous	Minor cognitive motor disorder
Corynebacterium infection	Mucocutaneous candidiasis
Corynebacterium sepsis	Mycobacterial infection
Cryptococcal cutaneous infection	Mycobacterium abscessus infection
Cryptococcal fungaemia	Mycobacterium avium complex immune restoration disease
Cryptococcosis	Mycobacterium avium complex infection
Cryptosporidiosis infection	Mycobacterium chelonae infection
Cutaneous coccidioidomycosis	Mycobacterium fortuitum infection
Cutaneous tuberculosis	Mycobacterium kansasii infection
Cytomegalovirus chorioretinitis	Mycobacterium marinum infection
Cytomegalovirus colitis	Mycobacterium ulcerans infection
Cytomegalovirus duodenitis	Mycotic endophthalmitis

Fungaemia	Presumed ocular histoplasmosis syndrome
Fungal abscess central nervous system	Proctitis herpes
Fungal endocarditis	Proctitis monilial
Fungal infection	Progressive multifocal leukoencephalopathy
Fungal oesophagitis	Prostatitis tuberculous
Fungal peritonitis	Pulmonary mycosis
Fungal sepsis	Pulmonary trichosporonosis
Fungal tracheitis	Pulmonary tuberculoma
Funguria	Pulmonary tuberculosis
Gastritis fungal	Pyelonephritis fungal
Gastritis herpes	Renal tuberculosis
Gastroenteritis cryptococcal	Respiratory moniliasis
Gastroenteritis cryptosporidial	Respiratory tract infection fungal
Gastrointestinal candidiasis	Retinitis histoplasma
Gastrointestinal fungal infection	Retroviral infection
Genital blister	Retroviral rebound syndrome
Genital herpes	Salmonella bacteraemia
Genital herpes zoster	Salmonella sepsis
Haemorrhagic pneumonia	Salmonellosis
Hepatosplenic abscess	Salpingitis tuberculous
HIV associated nephropathy	Silicotuberculosis
HIV cardiomyopathy	Sinusitis aspergillus
HIV enteropathy	Skin candida
HIV infection	Spleen tuberculosis
HIV infection CDC Group I	Splenic candidiasis
HIV infection CDC Group II	Splenic infection fungal
HIV infection CDC Group III	Stoma site candida
HIV infection CDC Group IV subgroup A	Stoma site infection
HIV infection CDC Group IV subgroup B	Superinfection fungal
HIV infection CDC Group IV subgroup C1	Superinfection mycobacterial
HIV infection CDC Group IV subgroup C2	Systemic candida
HIV infection CDC Group IV subgroup D	Systemic mycosis
HIV infection CDC Group IV subgroup E	T-cell lymphoma
HIV infection CDC category A	T-cell type acute leukaemia
HIV infection CDC category B	Thyroid tuberculosis
HIV infection CDC category C	Tongue fungal infection
HIV infection CDC group IV	Toxoplasmosis
HIV infection WHO clinical stage I	Tropical spastic paresis
HIV infection WHO clinical stage II	Tuberculoma of central nervous system

Opportunistic Infections: MedDRA Preferred Terms	
HIV infection WHO clinical stage III	Tuberculosis
HIV infection WHO clinical stage IV	Tuberculosis bladder
HIV peripheral neuropathy	Tuberculosis gastrointestinal
HIV wasting syndrome	Tuberculosis liver
Hepatic candidiasis	Tuberculosis of central nervous system
Hepatic infection fungal	Tuberculosis of eye
Hepatitis B	Tuberculosis of genitourinary system
Hepatitis C	Tuberculosis of intrathoracic lymph nodes
Hepatitis chronic persistent	Tuberculosis of peripheral lymph nodes
Hepatitis fulminant	Tuberculosis ureter
Hepatitis toxoplasmal	Tuberculous abscess central nervous system
Hepatitis viral	Tuberculous endometritis
Hepatitis virus-associated nephropathy	Tuberculous laryngitis
Hepatosplenic candidiasis	Tuberculous pleurisy
Herpes dermatitis	Tuberculous tenosynovitis
Herpes oesophagitis	Typhoid fever
Herpes ophthalmic	Varicella keratitis

## 6.2 Appendix B: Laboratory Parameters of Interest

Lab parameters of interest	Grade			
	1	2	3	4
HEMOGLOBIN decrease	Hemoglobin (Hgb) <LLN - 10.0 g/dL; <LLN - 6.2 mmol/L; <LLN - 100 g/L	Hgb <10.0 - 8.0 g/dL; <6.2 - 4.9 mmol/L; <100 - 80g/L	Hgb <8.0 g/dL; <4.9 mmol/L; <80 g/L; transfusion indicated	Life-threatening consequences; urgent intervention indicated
WHITE CELL COUNT decrease	<LLN - 3000/mm3; <LLN - 3.0 x 10e9 /L	<3000 - 2000/mm3; <3.0 - 2.0 x 10e9 /L	<2000 - 1000/mm3; <2.0 - 1.0 x 10e9 /L	<1000/mm3; <1.0 x 10e9 /L
TOTAL NEUTROPHILS ABSOLUTE COUNT	<LLN - 1500/mm3; <LLN - 1.5 x 10e9 /L	<1500 - 1000/mm3; <1.5 - 1.0 x 10e9 /L	<1000 - 500/mm3; <1.0 - 0.5 x 10e9 /L	<500/mm3; <0.5 x 10e9 /L
LYMPHOCYTES ABSOLUTE COUNT decreased	<LLN - 800/mm3; <LLN - 0.8 x 10e9 /L	<800 - 500/mm3; <0.8 - 0.5 x 10e9 /L	<500 - 200/mm3; <0.5 - 0.2 x 10e9 /L	<200/mm3; <0.2 x 10e9 /L
LYMPHOCYTES ABSOLUTE increased		>4000/mm3 - 20,000/mm3 ; >4-2 x 10e9 /L	>20,000/mm3; >20 x 10e9 /L	
PLATELET COUNT	<LLN - 75,000/mm3; <LLN - 75.0 x 10e9 /L	<75,000 - 50,000/mm3; <75.0 - 50.0 x 10e9 /L	<50,000 - 25,000/mm3; <50.0 - 25.0 x 10e9 /L	<25,000/mm3; <25.0 x 10e9 /L
CREATININE	>1 - 1.5 x baseline; >ULN - 1.5 x ULN	>1.5 - 3.0 x baseline; >1.5 - 3.0 x ULN	>3.0 baseline; >3.0 - 6.0 x ULN x ULN	>6.0 x ULN
SODIUM decrease	<LLN - 130 mmol/L		<130 - 120 mmol/L	<120 mmol/L;
SODIUM increase	>ULN - 150 mmol/L	>150 - 155 mmol/L	>155 - 160 mmol/L	>160 mmol/L
POTASSIUM decrease	<LLN - 3.0 mmol/L	<LLN - 3.0 mmol/L	<3.0 - 2.5 mmol/L	<2.5 mmol/L
POTASSIUM increase	>ULN - 5.5 mmol/L	>5.5 - 6.0 mmol/L	>6.0 - 7.0 mmol/L	>7.0 mmol/L

CALCIUM increase	>ULN - 11.5 mg/dL; >ULN - 2.9 mmol/L	>11.5 - 12.5 mg/dL; >2.9 - 3.1 mmol/L	>12.5 - 13.5 mg/dL; >3.1 - 3.4 mmol/L;	>13.5 mg/dL; >3.4 mmol/L
CALCIUM decrease	<LLN - 1.0 mmol/L	<1.0 - 0.9 mmol/L	<0.9 - 0.8 mmol/L	<0.8 mmol/L
PHOSPHORUS INORGANIC	<LLN - 2.5 mg/dL; <LLN - 0.8 mmol/L	<2.5 - 2.0 mg/dL; <0.8 - 0.6 mmol/L	<2.0 - 1.0 mg/dL; <0.6 - 0.3 mmol/L	<1.0 mg/dL; <0.3 mmol/L
ASAT (SGOT)	>ULN - 3.0 x ULN	>3.0 - 5.0 x ULN	>5.0 - 20.0 x ULN	>20.0 x ULN
ALAT (SGPT)	>ULN - 3.0 x ULN	>3.0 - 5.0 x ULN	>5.0 - 20.0 x ULN	>20.0 x ULN
GGT	>ULN - 2.5 x ULN	>2.5 - 5.0 x ULN	>5.0 - 20.0 x ULN	>20.0 x ULN
ALKALINE PHOSPHATASE	>ULN - 2.5 x ULN	>2.5 - 5.0 x ULN	>5.0 - 20.0 x ULN	>20.0 x ULN
BILIRUBIN, TOTAL	>ULN - 1.5 x ULN	>1.5 - 3.0 x ULN	>3.0 - 10.0 x ULN	>10.0 x ULN
CPK, TOTAL	>ULN - 2.5 x ULN	>2.5 x ULN - 5 x ULN	>5 x ULN - 10 x ULN	>10 x ULN
ALBUMIN	<LLN - 3 g/dL; <LLN - 30 g/L	<3 - 2 g/dL; <30 - 20 g/L	<2 g/dL; <20 g/L	
GLUCOSE	>ULN - 160 mg/dL; >ULN - 8.9 mmol/L	>160 - 250 mg/dL; >8.9 - 13.9 mmol/L	>250 - 500 mg/dL; >13.9 - 27.8 mmol/L	>500 mg/dL; >27.8 mmol/L
EST.CREATININE CLEARANCE	<LLN - 60 ml/min/1.73 m 	59 - 30 ml/min/1.73 m 	29 - 15 ml/min/1.73 m 	<15 ml/min/1.73 m 

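### SAP Appendix B grades low and high calcium on scales that cannot both fit the single calcium test, and its potassium-decrease row gives grades 1 and 2 the same range

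*SAP*

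**What the plan says.** SAP 6.2 (Appendix B) has two calcium rows, labelled only as calcium with a direction.

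- **Calcium increase**, in both units: grade 1 ">ULN - 11.5 mg/dL; >ULN - 2.9 mmol/L", grade 2 ">11.5 - 12.5 mg/dL; >2.9 - 3.1 mmol/L", grade 3 ">12.5 - 13.5 mg/dL; >3.1 - 3.4 mmol/L", and grade 4 above 13.5 mg/dL or 3.4 mmol/L.
- **Calcium decrease**, in mmol/L only: grade 1 "<LLN - 1.0 mmol/L", grade 2 "<1.0 - 0.9 mmol/L", grade 3 "<0.9 - 0.8 mmol/L", and grade 4 below 0.8 mmol/L.

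The laboratory panels (protocol 7.4.11, Table 2; SAP 4.10.8, Table 8) each contain one calcium entry. Neither lists a second test such as ionised calcium.

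The **potassium decrease** row gives "<LLN - 3.0 mmol/L" for grade 1 and the same for grade 2. Grade 3 is 3.0 to 2.5 mmol/L and grade 4 is below 2.5 mmol/L. The **potassium increase** row has distinct grades, starting with ">ULN - 5.5 mmol/L" for grade 1.

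SAP 4.10.8 tabulates the parameters of interest by time point and by Appendix B grade. It also plans shifts from baseline to worst grade, for parameters still to be chosen. SAP 4.5.3 keeps, among repeat laboratory values at one visit, the one with the worst CTCAE grade, and takes the later value in a tie.

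**The concern.** A grading table works only if the low and high cut-offs for an analyte sit on the same measurement scale, and if each value falls in exactly one grade. The two calcium rows appear to describe different measurements under one name. The first two potassium-decrease grades cannot be told apart. A programmer following Appendix B literally would produce calcium counts that are wrong in one direction, and grade 1 and grade 2 low-potassium counts that depend on an unstated coding choice. What is at stake is the reading of those safety tables.

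**Working it through.** **1. Is the calcium-increase row consistent within itself?** Divide mg/dL by mmol/L at each cut-off:

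- 11.5 / 2.9 = 3.97
- 12.5 / 3.1 = 4.03
- 13.5 / 3.4 = 3.97

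Allowing for mmol/L rounded to one decimal, any single factor from 3.97 to 4.03 fits all three. The row is sound.

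**2. Put the decrease row on that scale.** Multiply by 3.97-4.03:

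- 1.0 mmol/L = 3.97-4.03 mg/dL
- 0.9 mmol/L = 3.57-3.63 mg/dL
- 0.8 mmol/L = 3.17-3.22 mg/dL

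The row for high values leaves grade 1 at 11.5 mg/dL; the row for low values leaves it at about 4.0 mg/dL. The ratio 1.0 / 2.9 = 0.34 does not by itself prove a fault, so the next step measures the distance from LLN.

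**3. If results are on the increase-row scale.** The documents give no calcium LLN; assume 2.0-2.2 mmol/L. The fall needed to reach grade 2 is (LLN - 1.0) / LLN:

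| Assumed LLN (mmol/L) | Fall below LLN to leave grade 1 |
|---|---|
| 2.0 | 50.0% |
| 2.1 | 52.4% |
| 2.2 | 54.5% |

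As an illustration, take normally distributed results with assumed means of 2.1-2.4 and SDs of 0.10-0.20 mmol/L. The least favourable pair gives P(value < 1.0) = Φ((1.0 - 2.1) / 0.20) = Φ(-5.5) = 1.9 × 10⁻⁸. Grades 2-4 would be almost empty anywhere in this range.

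**4. If results are on the decrease-row scale.** The fault moves to the other row. A result would have to exceed 2.9 mmol/L, which is 2.9 times the 1.0 mmol/L boundary of the low row, to leave grade 1 for high calcium.

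**5. Potassium decrease.** With an assumed LLN of 3.5 mmol/L, values of 3.4, 3.2 and 3.0 each satisfy grades 1 and 2; 2.8 satisfies grade 3 only. Taking the worse grade empties grade 1; taking the first match empties grade 2. The same check on potassium increase, with an assumed upper limit of normal of 5.0 mmol/L, finds no overlap: 5.2 is grade 1, 5.7 grade 2 and 6.5 grade 3. Elsewhere Appendix B leaves an unused grade blank (grade 2 for low sodium, grade 1 for raised lymphocytes), so a repeated range is not its usual sign for no such grade.

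**6. The repeat-value rule.** If the grades in SAP 4.5.3 are those of Appendix B, take an assumed LLN of 2.1 or 2.2 mmol/L and calcium results of 1.5 and then 2.0 mmol/L at one visit (illustrative). Both are grade 1, so the tie goes to the later 2.0 and the more abnormal result leaves the visit summary.

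**7. A neighbouring cell.** Grade 2 for raised lymphocytes pairs an upper bound of 20,000/mm3 with an upper bound of 2 × 10e9/L. The grade 3 cell equates 20,000/mm3 with 20 × 10e9/L.

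**The case against.** The main counter-argument is that little depends on these rows, and most of it stands.

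- **No decision rule uses them.** Exclusion criterion 24 cites CTCAE v4.0 directly. The laboratory and ECG withdrawal and interruption criteria (protocol 5.4, 5.5.2 and Appendix 12.3) use liver chemistry, QTc and haematology. The laboratory-derived event of special interest in SAP Table 7 uses neutrophils. The distribution display for the Data Review Committee names neither calcium nor potassium.
- **The values stay visible.** SAP 4.10.8 summarises observed values and changes for every parameter, and lists abnormal results with reference limits. Protocol 7.4.5 has clinically significant abnormalities recorded as adverse events, subject to its exception for the underlying disease.
- **The analyte is unstated.** The documents do not say whether either row means total or ionised calcium. This weakens any claim about which row is wrong, but not the claim that both cannot apply to one test.
- **Text reading.** A merged potassium cell for grades 1 and 2, or a dropped digit in the lymphocyte cell, cannot be ruled out from extracted text. The calcium mismatch does not depend on this.

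A reader might infer that severe low calcium will be hidden, that low potassium cannot be graded at all, or that the shift tables are wrong. The documents support none of these. The first assumes the increase-row scale and ignores the value summaries and listings. The second overlooks grades 3 and 4, which are distinct. The third assumes that calcium or potassium will be selected for the shift table, which SAP 4.10.8 leaves open.

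**Conclusion.** The point holds within limits, and its severity is minor. One reported calcium result cannot be graded validly by both calcium rows, whichever analyte the laboratory measures. That low-calcium grades 2-4 would be almost empty is conditional: it requires results on the increase-row scale and rests on the assumed LLN of 2.0-2.2 mmol/L. Potassium decrease is ambiguous only from 3.0 mmol/L up to LLN.

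The effect is confined to the by-grade safety tables, to the choice among repeat values at a visit if Appendix B supplies the grade, and to the shift table if these parameters are chosen. Efficacy, sample size and the stopping criteria are untouched.

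**What to change.** In Appendix B:

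1. Name the calcium analyte that the central laboratory reports, and put both calcium rows on that scale using the CTCAE version the SAP cites (v4.0).
2. Give potassium decrease one programmable category for 3.0 mmol/L to LLN, and say how it is labelled in the tables.
3. Check the raised-lymphocyte grade 2 upper bound against the 20,000/mm3 in the same cell.

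The cost is a correction to a few appendix rows and the matching derivation code. No new data and no design change are needed.
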